10.3 Randomization

Randomization: Study participants at study inception are randomized through the Way to Health Platform using a random number generator and permuted block randomization with variable block sizes to force balance among treatment group assignments; variable block sizes will preclude prediction of treatment assignments by study staff. Randomization will be in a 1:1 ratio for each intervention compared to control and will be stratified by: (1) the employer site; (2) sex, and (3) degree of obesity at baseline (BMI 30-37.9 and 38-55 kg/m²), as baseline BMI may moderate treatment effects. Following randomization, the study coordinator will provide instructions about the control, incentive, or environmental arms.

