11.1 Statistical Considerations

Descriptive analyses

We will produce data summaries regularly using frequencies for categorical variables and means, medians, and ranges for continuous variables. We will assess data quality and examine distributional assumptions with graphical methods. To evaluate balance among groups achieved by randomization, we will compare baseline values of all variables across the 4 arms using appropriate tests.

General procedures

All primary analyses will be on an intent-to-treat basis including each participant in the group to which s/he was randomized, regardless of adherence to the assigned strategy. Given the high rates of missing data typical of weight loss studies, handling of missing data is an important issue. Primary analyses will use multiple imputation for the missing in-person weight outcome at 18 months, using the randomization strata (sex, employer, initial BMI), study arm and other baseline variables as predictors in the imputation model. Baseline variables will include age, race, income, education, marital status, household size, physical activities, eating behavior index, stages of change, SF-36 General Health, and baseline weight. Sensitivity analyses will be performed with imputation models that also use post-baseline data, , and recent weight loss trend before drop out, as well as an analysis that assumes that any participants for whom follow-up weight loss data are unavailable have had their weight return to baseline (weight at beginning of Pre Phase). Within each arm, this last assumption is likely to be conservative but this may not be the case in inter-arm comparisons, depending on the dropout rates in

the different arms and true follow-up weights of the dropouts. Thus, a key secondary analysis will consider the effect of differential dropout among the treatment arms. For this analysis, methods that address potential patterns of MNAR may be considered in the missing data imputation, such as pattern mixture models as appropriate. Finally, we will also consider a per-protocol type analysis, which examines the difference in the intervention arms in the complete case data.

Efficacy Analyses

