All hypotheses will be tested using two-sided, 0.05-level tests unless otherwise specified (notably the Holm testing approach will be used for the five primary hypotheses in Specific Aims 1-4). The primary analyses will be an unadjusted intent-to-treat analyses, using a t-test for differences in weight change from baseline to 18 months, as measured by the in-person weight, between each intervention group and the control group, and the combined compared to each single intervention, applying the Holm p-value correction for multiple comparisons testing. If weight change appears to be non-normally distributed in the blinded data, we will find an appropriate. Missing data will be handled as described above.

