Weight change between baseline and 18 months, with 95% confidence intervals (CIs), will be estimated for comparison with adjusted analyses. We will estimate regression models adjusted for the stratification variables (sex, employer, initial BMI) and other participant characteristics factors including age, race, income, and education. We will evaluate the evidence of confounding for other baseline variables (baseline weight, marital status, household size, physical activities- i.e total minutes of MVPA+walking/week, eating behavior index, stages of change, SF-36 General Health) using change in estimate criterion (10%). We will fit exploratory models of the repeated weight measurements that incorporate time as a polynomial function or using visit-specific indicator variables to determine the most parsimonious model that adequately describes the observed patterns, as necessary. Models will be built separately for the in-person and at home weight data. Models using the at-home weight data would be considered only as potential exploratory analyses comparing the 3 intervention arms, since at-home weights are not available for the control arm. We will investigate random-effects models that allow for baseline individual variability as well as variability in the changes in weights over time; an example is the following: $E(\text{weight}_{ij}) = \beta_0 + \beta_1 \text{Time}_j + \beta_2 \text{Group}_i + \beta_3 X_i + b_{0i} + b_{1i} \text{Time}_j$, where i indicates subject, j indicates assessment times, the parameters are fixed effects linking time, a treatment group vector, and a vector of other demographic or clinical covariates X_i to the outcomes, and b_{0i} and b_{1i} are random intercept and slope effects. Tests for significance of random effects will use likelihood ratio tests for nested models; we will compare models with different random effects structures using the maximized log-likelihoods and the Akaike Information Criterion (AIC). We will apply standard diagnostic techniques to assess model adequacy. We will use treatment by time interactions to assess whether the rate of change in weight differs by intervention arm. We hypothesize that incentives may be more effective among lower income individuals and will evaluate this using interaction terms of income with treatment group. We will explore differential effects by race and education and baseline levels of intrinsic motivation and stages of change. We will also consider other potential mediators, such as the home food and activity environment. To assess the sensitivity of treatment effect estimates to missing

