11.2 Power and Sample Size Considerations

We have designed the study with adequate power to detect differences in weight loss over an 18-month period. Our intervention should achieve its maximal impact in maintaining initial weight loss at the end of Phase II (month 18), when the incentive payments cease. To maintain the experiment-wide Type I error and guard against false conclusions of effectiveness, we will use the Holm multiple comparisons adjustment for test the 5 primary comparisons in Specific Aims 1-4 . If the interventions are as effective as hypothesized, the proposed sample size maintains greater than 90% power to show significance for each of the three intervention arms compared to control and greater than 80% power to show significance for the combined intervention group compared to each of the two interventions alone.

It is important to note that while we originally planned to recruit 328 participants, a small subset was unable to successfully set up their Withings scales post randomization due to Wi-Fi connectivity issues. Therefore, we increased our target sample size by the number of people who were unable to connect their Withings scales to the Way To Health platform (16 additional subjects), bringing our recruitment total to 344 participants. The final statistical analysis is adjusted for the stratification factors to account for any imbalances that may have occurred. We have previously communicated this information to the IRB and the members of the Data Safety and Monitoring Board (DSMB), who approved this approach. The following information outlines our original power calculations and sample size considerations.

We plan to recruit approximately one third of the participants required for the start of Phase I from each of our participating employers (IBC, SEPTA, and City of Philadelphia). Given the large number of potentially eligible employees, we can, if needed, easily increase the proportion of participants from any of these employers to meet recruitment targets. Participants will be randomized to our 3 intervention groups and the control group using a 1:1 ratio for the intervention arms. We built in a margin of 20% of

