our original target sample size of 328 for potential attrition before the 18-month assessment, resulting in an expected 260 participants (65 per arm) who are available for analysis at the end of Phase II. This sample size will provide us with greater than 90% power to detect a difference in weight change between baseline and the 18-month weigh-in of 5 kg between each single intervention group and the control group (primary outcomes for Specific Aims 1-3) and 87% power to detect a 3 kg difference between the combined group and either the incentive or environmental strategies groups (Specific Aim 4). Namely, we will have greater than 85% power for the 5 primary comparisons of interest for an expected weight change between months 0-18 of -8 kg, -5 kg and 0 kg in the combined, intervention and control groups, respectively (a net difference between single intervention and control groups of 5 kg, combined intervention and control groups of 8 kg, and 3kg between the single interventions and combined group) and assuming a standard deviation (S.D.) of weight loss of 5 kg. We will also have greater than 80% power to detect a difference of 4.6 kg in weight change between single intervention and control groups and 7.3 kg between the combined and control groups (primary outcomes for Specific Aims 1-3), while maintaining approximately 80% power for a 2.7 kg difference between the combined and each single intervention (Specific Aim 4). For our secondary outcomes (Specific Aim 5), we wish to compare the cost differences between each arm relative to the effectiveness measured by incremental weight loss achieved. We will calculate a point estimate of cost per kg of weight loss based on estimated inter-arm differences in weight loss and the incremental cost of the interventions, as described in C.3.d.ii.c. For weight loss at 18 months, given an expected incremental cost of \$810 (incentives) and incremental weight loss of 5 kg, 328 participants provide 80% power to detect a cost per kg lost of \$430 and greater than 90% power to detect a cost per kg lost of \$575. This study is primarily a test of the efficacy of these interventions. Due to resource constraints and because we do not yet know about intervention effectiveness, we did not power this study based on cost effectiveness analyses. Estimated detectable costs per kg are a function of wide confidence intervals due to sample size.

11.3 Measurement of effect:

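### The primary analysis is an unadjusted t-test in Section 11.1 but the final analysis is strata-adjusted in Section 11.2; under stratified randomization the unadjusted test is valid but conservative

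*Combined protocol and SAP*

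**What the plan says.** Three places in the current text bear on which analysis is the main one.

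- Section 11.1, Efficacy Analyses: "The primary analyses will be an unadjusted intent-to-treat analyses, using a t-test for differences in weight change from baseline to 18 months". This covers each intervention against control and the combined arm against each single intervention, with Holm over the five.
- Section 11.1, next paragraph: the unadjusted weight change with its confidence interval "will be estimated for comparison with adjusted analyses". Those adjusted analyses are "regression models adjusted for the stratification variables (sex, employer, initial BMI) and other participant characteristics factors including age, race, income, and education", and further baseline variables may enter by a 10% change-in-estimate rule.
- Section 11.2, in the paragraph on raising recruitment from 328 to 344: "The final statistical analysis is adjusted for the stratification factors to account for any imbalances that may have occurred".

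Section 10.3 says randomization is "stratified by: (1) the employer site; (2) sex, and (3) degree of obesity at baseline". Section 11.1 also plans multiple imputation "using the randomization strata (sex, employer, initial BMI), study arm and other baseline variables as predictors in the imputation model".

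For the two combined-versus-single comparisons (Aim 4), Section 11.2 states "87% power to detect a 3 kg difference between the combined group and either the incentive or environmental strategies groups" and "maintaining approximately 80% power for a 2.7 kg difference between the combined and each single intervention".

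**The concern.** There are two linked problems.

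**Which analysis is primary.** Holm needs one p-value per comparison. The text supports three sources: an unadjusted t-test, a model adjusted for the strata only (the plain reading of Section 11.2), and the larger Section 11.1 regression, whose covariate set is partly chosen from the data. If these disagree near a Holm threshold, the plan does not say which one decides. The Section 11.2 sentence gives its purpose as correcting imbalance. It follows the account of participants who could not connect their scales after randomization, and under Section 10.4 only the three intervention arms receive scales. A reader would therefore expect the main arm comparisons to be the adjusted ones.

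**Analysis against design.** Stratified blocks balance the arms on employer, sex and BMI class, so the arm difference varies less from trial to trial than under simple randomization. A t-test that omits the strata still counts the between-stratum variation as noise. If the strata are prognostic, its standard error is too large. The cost falls mainly on Aim 4, which has the least power in the plan.

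**Working it through.** **Inputs from the documents.** SD of weight change 5 kg; 65 analysable per arm; differences of 3 kg and 2.7 kg for Aim 4 (Section 11.2). Two-sided 0.05 with Holm over five tests (Section 11.1). Strata: 3 employers × 2 sexes × 2 BMI classes = 12 (Section 10.3).

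**Assumed input.** R², the share of weight-change variance explained by the strata, is not in the documents. Values of 0, 5%, 10% and 20% are used.

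**Step 1. Reproduce the plan's figures.** The comparisons with control are so well powered that Holm normally rejects those three first. The smaller of the two Aim 4 p-values then faces 0.05/2 = 0.025. The standard error is 5 × √(2/65) = 0.877 kg. The noncentral t with 128 df gives 87.4% at 3 kg (stated 87%) and 79.0% at 2.7 kg (stated approximately 80%). Both reproduce.

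**Step 2. Effect of stratification, by formula** (normal approximation).

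- Reported SE of the t-test = 0.877. True SE = 0.877 × √(1 − R²).
- Size at nominal 5% = 2 × [1 − Φ(1.96/√(1 − R²))].
- Unadjusted power = 1 − Φ((2.241 × SE_reported − d)/SE_true).
- Adjusted power = 1 − Φ(2.241 − d/SE_true).

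Example at R² = 10% and d = 2.7: SE_true = 0.877 × √0.9 = 0.832. Unadjusted: (2.241 × 0.877 − 2.7)/0.832 = −0.88, power 81.1%. Adjusted: 2.241 − 2.7/0.832 = −1.00, power 84.2%.

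| R² | Size of t-test | 3 kg: unadjusted vs adjusted | Loss (points) | 2.7 kg: unadjusted vs adjusted | Loss (points) |
|---|---|---|---|---|---|
| 5% | 4.4% | 88.7 vs 89.8% | 1.1 | 80.5 vs 82.0% | 1.6 |
| 10% | 3.9% | 89.3 vs 91.4% | 2.1 | 81.1 vs 84.2% | 3.1 |
| 20% | 2.8% | 90.6 vs 94.3% | 3.7 | 82.5 vs 88.5% | 6.0 |

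Losses are taken before rounding.

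**Step 3. Simulation of the planned procedure.** 328 randomized to four arms in permuted blocks of 4 and 8 within 12 strata, with additive stratum effects; 20% missing at random (328 × 0.8/4 = 65.6 completers per arm); 20 imputations from arm and strata; Rubin's rules; full Holm for power. The other baseline predictors in the planned imputation model were not simulated. The unadjusted analysis is a pairwise pooled t-test. The adjusted one is a linear model on all four arms plus employer, sex and BMI class.

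| R² | Null size at nominal 5%: unadjusted vs adjusted | Mean Aim 4 power, arm means 0/−4.6/−4.6/−7.3 kg | Mean Aim 4 power, arm means 0/−5/−5/−8 kg |
|---|---|---|---|
| 0 | 5.1 vs 5.1% | 82.7 vs 83.1% | 90.8 vs 91.1% |
| 5% | 4.3 vs 4.9% | 83.5 vs 85.2% | 91.5 vs 92.4% |
| 10% | 4.1 vs 5.1% | 85.3 vs 87.7% | 91.7 vs 93.2% |
| 20% | 3.1 vs 5.0% | 87.2 vs 91.3% | 93.9 vs 96.3% |

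These powers exceed those in Step 2 partly because Holm tests the last remaining comparison at the full 0.05. Comparisons with control exceed 99.8% throughout.

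**Step 4. Cross-check.** A complete-case simulation of one comparison at alpha 0.05, without imputation, gave unadjusted sizes of 4.6%, 4.2% and 3.4% at R² = 5%, 10% and 20%. Power at 3 kg was 92.6 vs 92.6%, 93.9 vs 95.0% and 94.3 vs 96.8%.

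**The case against.** The strongest reply is that only one sentence is loose. Section 11.1 is the only place that labels a primary efficacy test. The Section 11.2 sentence never uses that label, sits in a paragraph about the increase of 16 participants, and may mean the supporting regression. That reading is possible, but the text does not state it. The supporting regression also adjusts for more than the strata, so it does not match the Section 11.2 description.

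The second reply is that a valid test with adequate stated power is not an error, and that preferring an adjusted model is a matter of judgement. This is right as far as it goes. Under stratification the unadjusted power is at or slightly above the plan's own figures, and the loss exists only relative to the better model.

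The third reply is that R² is unknown, and this stands. The support in the plan is thin. Section 8.3 caps BMI to limit outliers in the weight result, and Section 10.3 justifies the BMI stratum by possible effect modification, which is not the same as prognosis. At the larger R² the formula also gives bigger losses than the simulation with imputation: 6.0 against 4.1 points at 2.7 kg, and 3.7 against 2.4 points at 3 kg, with R² = 20%.

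Finally, Section 11.2 reports the scale failures in the past tense, so the trial was already under way. Any change of primary model must precede sight of unblinded outcomes.

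**Conclusion.** The concern holds. The inconsistency does not depend on any assumption: both statements are in the body text and nothing reconciles them.

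The efficiency point depends on R². If the strata explain nothing, the two analyses are practically equal. At 5% to 10% the loss on Aim 4 is small, at most about 3 points. At 20% it is about 2 to 6 points, depending on the scenario and on whether formula or simulation is used. The unadjusted test errs towards too few rejections, so there is no inflation of type I error. The sample size needs no change, and conclusions against control would hardly be affected. This should be fixed, but it does not threaten the trial.

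**What to change.** In Section 11.1, define the primary analysis as a linear model of 18-month weight change on arm plus employer, sex and BMI stratum (30–37.9, 38–55). Fit it in each imputed dataset, combine by Rubin's rules, and let its five p-values enter Holm. Fix that covariate set with no optional additions, and date the change before unblinded outcomes are seen. Keep the unadjusted t-test as a sensitivity analysis and label the larger regression secondary. In Section 11.2, say that the strata-adjusted analysis is the primary one.

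If the sponsor prefers to keep the t-test as primary, Section 11.2 should say that the strata-adjusted analysis is secondary. That alone removes the inconsistency, at the efficiency cost shown above.

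Either route is a wording change. The strata are known for everyone from randomization, are already in the imputation model and already appear in a planned regression. No new data and no additional participants are needed.

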research is limited. Cross-sectional research indicates that having multiple environmental supports (stairways, facilities, equipment) at worksites is associated with meeting physical activity interventions. In addition to environmental changes to worksite structures, environmental re-engineering is a promising strategy and is being studied in several trials with a home environment focus. A recent study of environmental changes for weight gain prevention in worksites found no impact on body mass from environmental changes alone, perhaps due to limited strength of the interventions, deployment of single strategies in isolation, inadequate implementation, and because such studies included normal weight, overweight, and obese employees.

2.6 Cost of Obesity and Cost-effectiveness of Behavioral Interventions. Recent studies concluded that annual US expenditures attributable to overweight and obesity are between \$90 and \$100 billion. Among nationally representative cohorts, the average annual incremental cost of obesity is about \$1,308. Higher BMIs in young adulthood and middle age are associated with substantially higher Medicare expenditures in old age. Higher BMI also translates into significantly higher health care charges within 18 months, suggesting that health plans may find it cost effective to invest in behavior modification to lower health expenditures. Several economic assessments of behavioral interventions for weight loss have been published. The Diabetes Prevention Program, reported that, compared to placebo, the intensive lifestyle intervention had cost per QALY ratios ranging between \$32,000 and \$52,000, depending upon whether direct medical costs alone or direct and indirect costs were counted. Finkelstein et al. reported that the 1-year incremental cost per 1% reduction in 10-year CHD risk associated with an enhanced behavioral intervention was \$637.135. The substantial health and economic consequences of obesity highlight the importance of testing new approaches to maintenance of weight loss and the potential cost effectiveness of successful interventions.

3. Data Management and the Way to Health Platform

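### Holm is valid here and delivers the stated power, but it ignores the logical links among the five primary comparisons; a constrained step-down would recover some power if effects fall well short of plan

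*Combined protocol and SAP*

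**What the plan says.** Section 11.1 (Efficacy Analyses) sets the general rule that "All hypotheses will be tested using two-sided, 0.05-level tests unless otherwise specified", and adds that "the Holm testing approach will be used for the five primary hypotheses in Specific Aims 1-4". The primary tests are t-tests on weight change from baseline to 18 months "between each intervention group and the control group, and the combined compared to each single intervention", "applying the Holm p-value correction for multiple comparisons testing". That makes five: lottery, environmental and combined each against control (Aims 1–3), and combined against each single arm (Aim 4).

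Section 11.2 gives the purpose, "To maintain the experiment-wide Type I error and guard against false conclusions of effectiveness", and repeats that "we will use the Holm multiple comparisons adjustment for test the 5 primary comparisons". With 65 analysable participants per arm, SD 5 kg and mean changes of −8, −5 and 0 kg (combined, single arm, control), it states more than 90% power against control and "87% power to detect a 3 kg difference between the combined group and either the incentive or environmental strategies groups". It also gives a smaller set of differences (4.6, 7.3 and 2.7 kg), with about 80% for the 2.7 kg contrast. Section 5.2 says that the power figures assume Holm. The document names no procedure that uses the links between the hypotheses, and gives no power for effects much below plan.

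**The concern.** Holm divides 0.05 by 5, 4, 3, 2 and 1 in turn. Each divisor is the number of hypotheses not yet rejected, and so allows for all of them being true at once. With five contrasts built from four means, that is often impossible. If combined and control differ, for example, a single arm cannot equal both.

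Where the divisor exceeds the largest number of hypotheses that can still be true, the test is stricter than section 11.2's purpose requires, and power is lost with no gain in protection. At stake is power for Aims 1, 2 and 4 if the true effects are well below those planned, which is when power is scarce.

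**Working it through.** **Inputs.** From section 11.2: n = 65 per arm, SD 5 kg, planned differences of 5, 5 and 8 kg from control. From section 11.1: two-sided family-wise 0.05, five pairwise t-tests. Means below are written as control/lottery/environmental/combined weight loss in kg.

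**Reproducing the plan's figures.** Standard error of a difference = 5 × √(2/65) = 0.877 kg. For 3 kg, 3/0.877 = 3.420. At two-sided 0.025 (0.05/2, Holm's fourth level) the critical value is 2.241, so power ≈ Φ(3.420 − 2.241) = 88.1%, or 87.4% with the noncentral t. For 2.7 kg the same steps give 79.9% and 79.0%. At 0.05 the 3 kg power is 92.4% and at 0.01 it is 78.8%, so the stated 87% is the 0.025 figure. Power for 5 kg is at least 99.9% even at 0.01. The plan's statements hold.

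**Which hypotheses can be true together.** Every way of setting some of the four means equal was listed.

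- Any four of the five equalities link all four arms, so the fifth must follow. The number true is 0, 1, 2, 3 or 5, never 4.
- Three can be true in two ways: lottery = control = combined, or environmental = control = combined. Both include combined = control.
- Once any one hypothesis is false, at most 3 of the other four are true. Once combined = control is false, at most 2 are.

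Holm's second divisor of 4 is therefore never needed. After combined versus control is rejected, 2 suffices where Holm uses 4 and then 3. Shaffer's divisors are never larger than Holm's.

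**Size of the loss.** Pairwise t-tests were simulated with 60,000 trials per row, except the 4.6/4.6/7.3 row (100,000), with complete data and equal SDs. Each cell is Holm → Shaffer.

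| True means | Share of plan | Single arm vs control | Combined vs single arm |
|---|---|---|---|
| 0/5/5/8 | 100% | >99.9%, identical | 91.1%, identical |
| 0/4.6/4.6/7.3 | plan's smaller set | 99.9%, identical | about 84%, identical |
| 0/3.5/3.5/5.6 | 70% | 96.0% → 96.4% | 60.0% → 60.3% |
| 0/3/3/4.8 | 60% | 86.6% → 88.6% | 44.1% → 45.4% |
| 0/2.5/2.5/4 | 50% | 67.9% → 72.8% | 27.6% → 30.5% |
| 0/2/2/3.2 | 40% | 43.2% → 49.8% | 15.5% → 19.1% |

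Separate runs of the half-effect row gave 67.4–67.9% under Holm and 72.3–72.8% under Shaffer. The 91.1% in the first row exceeds 87% because the last contrast is sometimes tested at 0.05.

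With 344 enrolled and 20% lost (344 × 0.8/4 ≈ 69 per arm), the half-effect figures for single arm versus control are 71.1% → 75.7%.

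**Error control.** With all means equal, family-wise error was 4.2% under both procedures. At 0/3/3/3 it was 3.6% under Holm and 4.4% under Shaffer. The tightest case is two separate true equalities, such as 0/5/0/5. Both are then tested at about 0.025 and theory gives 1 − 0.975² = 4.9% under either procedure. Counting wrong-direction claims as errors, Shaffer's rate stayed at or below 5.0%.

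**The case against.** The case for leaving the plan alone is substantial. Holm is valid under any dependence and meets the stated purpose. No figure is wrong, and nothing is lost at either set of effects that the plan considers. A 5-point gain needs effects to be halved, and Aim 4 is then badly underpowered under either method. Choosing between two valid procedures can be called a matter of taste. All of this stands, and it makes the point an improvement rather than an error.

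Timing also matters. Section 11.2 describes scale-connection failures after randomisation and a target already raised to 344, so the trial was under way. Section 13.2 has the DSMB assess study outcomes every six months, with principal investigators as non-voting members. A move to a more liberal procedure must be shown to have been made blind. That is a condition on the change, not a reason against it.

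Four stronger readings are tempting, and the documents do not support them.

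- *Holm assumes the hypotheses are independent or unrelated.* It does not; it only leaves their logical links unused.
- *The stated 87% needs both single arms to beat control.* It does not. Holm reaches 0.025 after any three rejections. For combined versus lottery these can be combined versus control, combined versus environmental and lottery versus control.
- *The null worksite result described in section 2.5 shows where Holm would hurt.* If the environmental arm does nothing and the other means hold (0/5/0/8), the two procedures give the same power, about 87.5% for combined versus lottery.
- *Shaffer restores the stated 87%.* The plan states 87% for its planned effects, where Holm already delivers it.

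**Conclusion.** The point holds as a matter of efficiency. Holm's second level, and its third once combined versus control is rejected, are stricter than family-wise control needs. The cost is zero at 5/5/8 kg and at 4.6/4.6/7.3 kg, and under half a point at 70% of plan. For single arm versus control it is about 2 points at 60% of plan and about 5 at half. For each Aim 4 test it is about 3 points at half.

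These sizes assume 65 per arm, SD 5 kg in every arm, complete data and effects scaled by a common factor; multiple imputation was not simulated. The logic assumes that the tests are of equality of means. Section 4 words the hypotheses as minimum differences, but the t-tests in section 11.1 and the power in section 11.2 are for any difference.

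**What to change.** By amendment before unblinding, replace Holm in sections 11.1 and 11.2 with Shaffer's logically constrained step-down on the same five p-values. Order the p-values and test the smallest at 0.05/5. At each later step divide 0.05 by the largest number of remaining hypotheses that can be true together given those already rejected, and stop at the first non-rejection. Put the divisors in the SAP:

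| Already rejected | Shaffer | Holm |
|---|---|---|
| None | 5 | 5 |
| Combined–control only | 2 | 4 |
| Any other one | 3 | 4 |
| Lottery–control and combined–lottery, or environmental–control and combined–environmental | 3 | 3 |
| Any other two | 2 | 3 |
| Three, including combined–control | 2, or 1 if the three are all the contrasts among control, combined and one single arm | 2 |
| Three, without combined–control | 1 | 2 |
| Four | 1 | 1 |

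The cost is a slightly longer description, a few lines of code and a record that the change was made blind. It needs no new data or participants, and the imputation-based p-values enter exactly as they would under Holm. One condition must be written in: section 11.1 allows another analysis if weight change is non-normal, and any replacement must also test equalities for which these constraints hold, a condition that Holm does not impose.
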